3.2.1.3. Dose-Limiting Toxicities (DLT)

A DLT is defined as any TEAE not attributable to disease or disease-related processes or to concomitant medications or procedures that occurs during the DLT-evaluation period (Cycle 0, Day 1 to Cycle 1, Day 21 of Dose Escalation) and is Grade 3 or above, according to NCI-CTCAE version 5.0, with the exceptions as defined below.

For hematological toxicities, a DLT is defined as follows:

Hematologic Dose-Limiting Toxicities (DLT) NCI-CTCAE version 5.0		
Hematological toxicity	NCI-CTCAE Grade	CTCAE version 5.0 Definition
Neutrophil count decreased	4 (Lasting > 7 days or neutrophil count decreased that requires supportive therapy with myeloid growth factors)	< 500/mm ³ ; < 0.5 × 10 ⁹ /L
Febrile neutropenia	≥ 3	Grade 3: ANC < 1000/mm ³ with a single temperature of > 38.3°C or a sustained temperature of ≥ 38°C for more than one hour Grade 4: Life-threatening consequences; urgent intervention indicated
Anemia	4	Life-threatening consequences; urgent intervention indicated
Platelet count decreased	≥ 3 Lasting > 7 days or with clinically significant hemorrhage	Grade 3: < 50,000 – 25,000/mm ³ ; < 50.0 – 25.0 × 10 ⁹ /L Grade 4: < 25,000/mm ³ ; < 25.0 × 10 ⁹ /L
Lymphocyte count decreased	4 Lasting ≥ 14 days	< 200/mm ³ ; < 0.2 × 10 ⁹ /L
Any	5	Death

For hepatic organ toxicities, a DLT is defined as follows:

Hepatic Dose-Limiting Toxicities (DLT) NCI-CTCAE version 5.0		
Hepatic Organ Toxicity	NCI-CTCAE Grade	CTCAE version 5.0 Definition
Serum aspartate aminotransferase (AST) increase	4	> 20.0 × the upper limit normal (ULN) if baseline was normal; > 20.0 × baseline if baseline was abnormal
Serum alanine aminotransferase (ALT) increase	4	> 20.0 × ULN if baseline was normal; > 20.0 × baseline if baseline was abnormal
AST or ALT increased	3 Lasting >5 days	> 5.0 – 20.0 × ULN if baseline was normal; > 5.0 – 20.0 × baseline if baseline was abnormal
ALT or AST increased $\geq 3.0 \times$ ULN with simultaneous TBL increased $\geq 2.0 \times$ ULN	Not applicable	Not applicable
Any	5	Death

For pulmonary toxicities, a DLT is defined as any of the following:

Pulmonary Dose-Limiting Toxicities (DLT) NCI-CTCAE version 5.0		
Pulmonary Toxicity	NCI-CTCAE Grade	CTCAE version 5.0 Definition
Confirmed interstitial lung disease (ILD)	1	Asymptomatic; clinical or diagnostic observations only; intervention not indicated
	2	Symptomatic; medical intervention indicated; limiting instrumental activities of daily living (ADL)
	3	Severe symptoms; limiting self care ADL; oxygen indicated
	4	Life-threatening respiratory compromise; urgent intervention indicated (eg., tracheotomy or intubation)
	5	Death
Any other pulmonary toxicity	≥ 3	Grade 3: Severe or medically significant but not immediately life-threatening; hospitalization or prolongation of

		existing hospitalization indicated; limiting self care ADL Grade 4: Life-threatening consequences; urgent intervention indicated Grade 5: Death
--	--	---

For non-hematological, non-hepatic, or non-pulmonary organ toxicities (ie, any other Grade ≥ 3 non-hematologic, non-hepatic, non-pulmonary toxicities including Grade 5 events), a DLT is defined as any of the following:

Dose-Limiting Toxicities (Non-Hematologic, Non-Hepatic, Non-Pulmonary Toxicities)		
DLT	NCI-CTCAE Grade	CTCAE version 5.0 Definition
Symptomatic heart failure	2	Symptoms with moderate activity or exertion
	3	Symptoms at rest or with minimal activity or exertion; hospitalization; new onset of symptoms
Left ventricular ejection fraction (LVEF)	3	Resting ejection fraction (EF) 39 – 20%; $\geq 20\%$ drop from baseline
Endocrine toxicities	≥ 3 Which do not resolve in ≤ 14 days	Grade 3: Severe or medically significant but not immediately life-threatening; hospitalization or prolongation of existing hospitalization indicated; limiting self care ADL Grade 4: Life-threatening consequences; urgent intervention indicated

The following TEAEs are considered DLTs
Thrombocytopenia requiring transfusion. Anemia requiring transfusion Inability to complete at least 75% of the prescribed doses (ie, at least 42 doses of DS-1205c and 16 doses of gefitinib) in the 7 days of Cycle 0 and the 21 days of Cycle 1 as a result of Grade ≥ 2 AE not attributed to disease.

The following TEAEs are NOT considered DLTs:

The following TEAEs are NOT considered Dose Limiting Toxicities		
TEAE	NCI-CTCAE Grade	CTCAE version 5.0 Definition
Fatigue	3 Lasting \leq 7 days	Fatigue not relieved by rest, limiting self care ADL
Nausea	3 That resolves to \leq grade 2 in 48 hours	Inadequate oral caloric or fluid intake; tube feeding, TPN, or hospitalization indicated
Vomiting	3 That resolves to \leq grade 2 in 48 hours	Tube feeding, TPN, or hospitalization indicated
Diarrhea	3 That resolves to \leq grade 2 in 48 hours	Increase of \geq 7 stools per day over baseline; hospitalization indicated; severe increase in ostomy output compared to baseline; limiting self care ADL
Anorexia	3 That resolves to \leq grade 2 in 48 hours	Associated with significant weight loss or malnutrition (eg., inadequate oral caloric and/or fluid intake); tube feeding or TPN indicated
Isolated laboratory findings not associated with signs or symptoms, including		

 Grade 3 or 4 serum ALP increased, hyperuricemia, serum amylase increased, lipase increased, or grade 3 hyponatremia, lasting $<$ 72 hours 		
Lymphocyte count	3	$< 500 - 200/\text{mm}^3$; $< 0.5 - 0.2 \times 10^9 / \text{L}$
Subjects missing more than 25% of scheduled doses in Cycle 0 and Cycle 1 for reasons not related to AEs (eg, noncompliance) will not be evaluable for DLT.		

Management of study drug-related AEs will be as per treating physician discretion and institutional guidelines. See Section 5.5 for information regarding the use of concomitant medications.

3.2.1.3.1. TEAEs During Cycle 0

In the event of a TEAE within Cycle 0 that may delay the start of Cycle 1, Day 1, Investigators should contact the Sponsor medical monitor or designee for guidance. Investigators should refer to Section 5.4 for information on interruptions of dose.

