3.2.1.2. Cycle 1 and Beyond (Combination Therapy)

In Cycle 1 and beyond, DS-1205c will be taken BID in combination with 250 mg QD of gefitinib in 21-day cycles, as outlined in detail in the Schedule of Events, Dose Escalation, (Cycle 1 and Beyond) ([Table 6.2](#)).

Dose escalation of DS-1205c to determine the RDE will be guided by the modified Continuous Reassessment Method (mCRM) using a Bayesian logistic regression model (BLRM) following the escalation with overdose control (EWOC) principle (Section [11.11](#)). The logistic regression model for the dose-response (DLT rate) relationships will include 2 parameters: the intercept and slope. The DLT-evaluation period is defined as the 7 days of Cycle 0 plus the 21 days of Cycle 1 (28 days total). A DLT-evaluable subject is defined as a subject who has received DS-1205c and either has completed minimum safety evaluation requirements over the DLT-evaluation period or has experienced a DLT during the DLT-evaluation period. After at least 3 DLT-evaluable subjects of each cohort complete DLT evaluation, posterior distributions of DLT rate will be derived for all dose levels based on the BLM using DLT outcome data from all assessed doses and a pre-specified prior distribution for the model parameters. The EWOC principle requires that the mCRM-recommended dose for the next cohort of subjects is the one with the highest posterior probability of the DLT rate in the target DLT rate interval with the overdose control constraint for excessive or unacceptable toxicity.

As an exception, the model will be reevaluated before enrollment of any additional subjects to the cohort if 2 DLT-evaluable subjects in the cohort experience DLT before the enrollment of the third subject. Enrollment of subjects to a new higher-dose cohort requires completion of DLT evaluation of at least 3 subjects treated in the current cohort. Subjects who have neither completed DLT evaluation nor experienced DLT will not be included in a BLM update. In the event when subjects in the previous cohort experience DLTs after enrollment of subjects to a new cohort has begun, dose level assignment of the next subject in the new cohort will be based on an updated BLM using DLT outcome data from all assessed doses. Subjects already receiving treatment will continue treatment at their assigned dose level or per dosing modification guidelines outlined in Section [5.4](#).

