6. STUDY PROCEDURES

6.1. Dose Escalation

In consideration of the subject's safety, the subjects will be hospitalized from Day 2 (Cycle 0, Day 2) to Day 30 (Cycle 2, Day 2) in Dose Escalation to allow for careful safety monitoring. However, temporary discharge or leave may be permitted at the Investigator's discretion after Day 15 (Cycle 1, Day 8), taking the subject's safety into consideration. Investigator should examine the subject carefully before granting temporary discharge or leave, and the study site should train the subject about an emergency contact.

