- Obtain blood samples for PK analysis for both DS-1205a and gefitinib at all specified time points within [Table 6.2](#). All PK blood draws should be performed as close as possible to scheduled time. When an ECG is performed at the same time point, the PK specimen should be taken immediately after completion of the ECG. Time window for collection time points: 2 hours (for pre-dose), ±15 minutes (for hours 1 to 10 post-dose), and ±2 hours (for 24 hours post-dose) of nominal times.
- Obtain blood sample for Exploratory Blood cfDNA pre-dose. As a general rule, this procedure should be conducted after ECG measurement.
- Obtain blood sample for Exploratory Blood Biomarker pre-dose. As a general rule, this procedure should be conducted after ECG measurement.
- Perform a complete physical examination, including weight (Section 9.11), and assess and record the functional status using the ECOG PS scale (Section 17.4).
- Ophthalmologic evaluation should be performed within 7 days of the scheduled visit. Assessments should include visual acuity testing, slit lamp examination, fundoscopy, and tonometry (Section 9.12).

- Perform either ECHO or MUGA within 7 days of the scheduled visit. The same test must be used for the subject throughout the study (Section 9.12).
- Assess AEs/SAEs (Section 9).
- Record concomitant medications.

After completion of 10-hour post-dose PK blood sample collections, subjects should be given dinner in the clinic. Dinner should be started approximately 30 minutes prior to dosing and should be completed before dosing. Subjects should receive the evening dose of DS-1205c in the clinic with 240 mL of water.

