6.1.3.6. Chest Radiograph for Safety Evaluation (Dose Escalation)

- Investigator should perform chest radiograph in Cycle 0 Day -1, Cycle 2, Day 1 and Cycle 4, Day 1 (± 2 days) for safety evaluation.

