- s. ECHO or MUGA should be performed on Cycle 2, Day 1 (7 days); Cycle 4, Day 1 (7 days), and on Day 1 of every 4 cycles (7 days) thereafter, and at EOT (7 days). The same test must be used for the subject throughout the study. Investigators must ensure results of ECHO/MUGA are available for review prior to dosing on corresponding cycle visits.

[figure not shown]
- t. On study biopsy is optional on Cycle 1, Day 15 (+7 days). Consent for this biopsy should be documented in the tissue consent portion of the appropriate ICF. Tumor biopsy may be obtained from primary tumor or metastatic site.
- u. EOT tumor biopsy is optional. Tumor biopsy should be obtained from primary tumor or metastatic site, preferably from a site of recent radiographic progression, within 30 days of the last dose of study drug, and prior to starting any new anticancer treatment.
- v. All clinical AEs occurring after the subject signs the Appropriate ICF and up to F/U visit (30 days [+7 days] after the final dose of study treatment, or before starting new anticancer treatment, whichever comes first) should be reported.

CCI

[figure not shown]
CCI

CCI

CCI

CCI

CCI

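### The DLT window closes on Day 28 with no on-treatment LVEF test or chest film required by then, and the protocol does not say how a Cycle 2 Day 1 finding counts

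*Combined protocol and SAP*

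**What the plan says.** Section 3.2.1.2 sets the window: "The DLT-evaluation period is defined as the 7 days of Cycle 0 plus the 21 days of Cycle 1 (28 days total". Section 3.2.1.3 counts an event as a DLT only if it is one "that occurs during the DLT-evaluation period (Cycle 0, Day 1 to Cycle 1, Day 21 of Dose Escalation". The DLT tables there include a Grade 3 fall in LVEF and confirmed ILD from Grade 1 upwards. Grade 1 is described as "Asymptomatic; clinical or diagnostic observations only; intervention not indicated".

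The tests that could show these are scheduled later. Footnote s of Table 6.2 says "ECHO or MUGA should be performed on Cycle 2, Day 1", and 6.1.3.3 says "Perform either ECHO or MUGA within 7 days of the scheduled visit". For chest imaging, 6.1.3.6 says "Investigator should perform chest radiograph in Cycle 0 Day -1, Cycle 2, Day 1 and Cycle 4, Day 1". The only earlier ECHO/MUGA is at screening. The only earlier chest film is the baseline one on Cycle 0 Day -1.

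On escalation, 3.2.1.2 says "Enrollment of subjects to a new higher-dose cohort requires completion of DLT evaluation of at least 3 subjects treated in the current cohort". A subject without a DLT is evaluable on meeting minimum safety evaluation requirements (3.2.1.2), which are not defined anywhere. For such a subject the DLT-Evaluable Set in 11.2 asks for 75% of the Cycle 1 doses and names no assessment.

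The visit lists for the Cycle 0 dosing days and for Cycle 1 (6.1.2.2 to 6.1.3.2) tell the site to decide whether adverse events are DLTs. The Cycle 2 Day 1 list (6.1.3.3) asks only for assessment of adverse events.

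**The concern.** Some named DLTs may be silent. A fall in ejection fraction or Grade 1 ILD can be present without symptoms and come to light only when a test is done. If that test comes after the window has closed, and no rule says how its result counts, the subject may be scored as free of DLT although the toxicity was never looked for on treatment.

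The Bayesian logistic regression model (BLRM) takes only DLT yes or no. Determining the recommended dose for expansion (RDE) is part of the primary objective, and cohorts start at three subjects, so each classification carries weight. Two sites could also classify the same Cycle 2 Day 1 result differently. Neither risk is remote on the protocol's own account: heart findings were seen in monkeys (1.1.2.4), and ILD is acknowledged for gefitinib (9.3.3).

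**Working it through.** **Day count.** The stated window reproduces: 7 + 21 = 28 days. Cycle 0 is Days 1 to 7 and Cycle 1 is Days 8 to 28, so Cycle 1 Day 15 is Day 22 and Cycle 2 Day 1 is Day 29. Section 6.1 uses the same calendar ("hospitalized from Day 2 (Cycle 0, Day 2) to Day 30 (Cycle 2, Day 2"). The 75% dose counts in 3.2.1.3 agree: 0.75 × 28 × 2 = 42 doses of DS-1205c, and 0.75 × 21 = 15.75, rounded up to 16 doses of gefitinib.

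**What the schedule assures by Day 28**

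| Test | On-treatment timing | Required by Day 28? |
|---|---|---|
| ECHO/MUGA | Cycle 2 Day 1 with 7 days' allowance: about Days 22–29 | No |
| Chest film | Cycle 2 Day 1 ± 2 days: Days 27–31 | No |
| Tumor CT | 6 weeks ± 7 days from Day 8: Day 50, range 43–57 | No |
| Thyroid | Cycle 0 Day 7 or Cycle 1 Day 1 pre-dose, then Cycle 2 Day 1 ± 1 day | Yes on monotherapy; no on the combination |
| Hematology, chemistry | Repeatedly to Cycle 1 Day 15 (Day 22 ± 1), then Cycle 2 Day 1 ± 1 day | To about Day 22; no required draw on nominal Days 23–28 |

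Two readings are assumed. The unsigned 7 days for ECHO/MUGA is taken as before the visit, because footnote s wants the result before dosing. The ± 2 days is taken to apply to the Cycle 2 film as well as the Cycle 4 film.

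The main gap is therefore LVEF and asymptomatic ILD. Late laboratory toxicity and thyroid function on the combination are lesser gaps.

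**Effect of one uncounted event.** Inputs from 11.11:
- Model: logit π(d) = log α + β log(d/800), with d in mg per dose.
- Prior for (log α, log β): bivariate normal, means (-1.1493, -0.5514), SDs (2.0739, 1.5228), correlation -0.1943.
- Rule: among doses with P(DLT rate > 0.33) < 0.25, take the one with the highest probability in 0.16–0.33.

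Numerical integration gives prior medians of 8.0% at 200 mg and 24.1% at 800 mg, against the stated 8% and 24.5% (both approximate), so the model is reproduced. The DLT counts below are illustrative.

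| Data | P(DLT rate > 0.33) | Doses passing |
|---|---|---|
| 0/3 at 200 | 0.037 at 200; 0.206 at 800 | all four |
| 1/3 at 200 | 0.368 at 200 | none |
| 0/3 at 200, 0/3 at 400 | 0.016 at 400; 0.049 at 600; 0.127 at 800 | all four |
| 0/3 at 200, 1/3 at 400 | 0.169 at 400; 0.292 at 600; 0.38 at 800 | 200 and 400; model picks 400 |
| 0/3 at 200 and 400, 0/3 at 600 | 0.069 at 800 | all four |
| 0/3 at 200 and 400, 1/3 at 600 | 0.115 at 600; 0.26 at 800 | up to 600; model picks 600 |

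In each pair, one event in three decides whether some or all doses stay admissible.

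**The case against.** A reader might infer that an LVEF fall first seen pre-dose on Cycle 2 Day 1 is dated Day 29 and so is not a DLT. The documents do not say that. The definition turns on when an event occurs, not when it is detected, and such a fall follows only dosing within the window. An investigator could place its onset there. The classification is open, not exclusionary.

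A reader might also infer that the schedule does not look for laboratory or thyroid DLTs in the window. That goes too far. Blood is drawn on Cycle 0 Days 2, 6 and 7 (or Cycle 1 Day 1) and Cycle 1 Days 4, 8 and 15. The endocrine DLT is defined by clinical severity and failure to resolve within 14 days, in subjects who are hospitalized, with leave possible after Day 15. Similarly, the pulmonary DLT is confirmed ILD: a film is only a trigger for work-up, and SpO2 and physical examination are done during Cycle 1.

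Nor do the documents support the claim that the final dose will be too high. The Sponsor chooses the next dose using adverse events and toxicity profiles as well as the model (3.2.1.2), safety review meetings take part (3.2.1.4), and the RDE draws on safety data from Cycle 1 onwards (3.2.1.6). Section 3.2.1.2 also provides a model update if DLTs appear in the previous cohort after a new one opens. Finally, the calculation shows what any one missed DLT does. After 0/3 at 200 mg alone the rule already selects 800 mg, so a stepwise path assumes Sponsor restraint beyond the model.

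All of this stands and narrows the point. It does not close it. Discretion does not correct the model's input, and the late update helps only if the event is accepted as a DLT, which is the question left open.

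**Conclusion.** The point holds as a gap in how DLT evaluation is completed. A subject can be scored as free of DLT, and a higher cohort can open, with no on-treatment LVEF test or chest image, because the first of each is nominally one day after the window closes and nothing ties completion of DLT evaluation to them. Laboratory toxicity arising after about Day 22 and the absence of a required thyroid test on the combination are secondary.

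One uncounted event can change the model's recommendation: in the 400 mg example, P(DLT rate > 0.33) at 600 mg is 0.049 rather than 0.292. Where an event goes uncounted, the model's error is towards higher doses. That result rests on illustrative counts and on cohorts of three. The documents give no basis for estimating how often an event would be visible only at Cycle 2 Day 1, so no overall bias in the RDE can be claimed.

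**What to change.** Reconcile 3.2.1.2, 3.2.1.3, 6.1.3.3, 6.1.3.6, Table 6.2, 11.2 and 11.11.3 as follows.

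- Define the minimum safety evaluation for a subject scored as free of DLT so that it includes the already scheduled Cycle 2 Day 1 pre-dose assessments (ECHO/MUGA, chest film, laboratory tests), reviewed before the model update and before a higher cohort opens. Carry the same requirement into the DLT-Evaluable Set.
- State how a finding first seen at those assessments is classified for the DLT window.
- Add the DLT-determination step to the Cycle 2 Day 1 list in 6.1.3.3.
- Align the chest film's ± 2-day window, which now runs to Day 31, with this rule.

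Footnotes r and s of Table 6.2 already require ophthalmology and ECHO/MUGA results before dosing at that visit. Only the unsigned 7-day wording in 6.1.3.3 needs to match them.

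Cost: no test is added. Each cohort decision waits about one to three days (Day 29 to Day 31 instead of Day 28), and a few more events may count as DLTs. Under 6.1, subjects are already hospitalized or on permitted leave to Day 30.

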11.2. Analysis Sets

- Enrolled Analysis Set will include all subjects who sign the ICF of the study.
- FAS will include all subjects in the Enrolled Analysis Set who received at least one dose of DS-1205c and who had baseline and post-treatment evaluable tumor assessments.
- DLT-Evaluable Set will include subjects enrolled in Dose Escalation who had at least one DLT during the 7 days of Cycle 0 or the 21 days of Cycle 1, or did not have a DLT but received at least 75% of the doses in the 21 days of Cycle 1.
- Safety Analysis Set will include all subjects in the Enrolled Analysis Set, who received at least one dose of DS-1205c. Four groups of subjects will be identified within the Safety Analysis Set: (1) subjects in Dose Escalation, (2) subjects in Dose Expansion, (3) subjects treated at the dose level of RDE, and (4) all treated subjects in the study.
- PK Analysis Set will include all subjects in the Enrolled Analysis Set who received any amount of the study drugs and have sufficient plasma concentration data to characterize PK of DS-1205a or gefitinib.

- Concentration-QTc Analysis Set will include all subjects who are in the Safety Analysis Set with at least one pair of postdose plasma concentration data and QTc data from the same timepoint. The concentration-QTc Analysis Set will be used for the concentration-QTc analysis.
- Biomarker Analysis Set will include all subjects in the Enrolled Analysis Set who received any amount of study drugs and who had the baseline tissue biopsy assessment and, where applicable, at least 1 post-treatment blood sample assessment for biomarkers.

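### One row of Section 3.2.1.3 makes subjects who miss more than 25% of doses for non-AE reasons unevaluable for DLT, with no exception for a subject who already had a DLT, contradicting Sections 3.2.1.2 and 11.2

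*Combined protocol and SAP*

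**What the plan says.** Section 3.2.1.3 ends with a table of events that do not count as DLTs. Its last row is about subjects, not events: those whose missed doses exceed a quarter "of scheduled doses in Cycle 0 and Cycle 1 for reasons not related to AEs (eg, noncompliance) will not be evaluable for DLT". Nothing limits the row to subjects without a DLT.

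Three other statements treat the DLT subject differently.

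- **Evaluability, Section 3.2.1.2 (and the synopsis).** A DLT-evaluable subject is one who, after taking DS-1205c, "either has completed minimum safety evaluation requirements over the DLT-evaluation period or has experienced a DLT during the DLT-evaluation period". A DLT is sufficient on its own.
- **Model update, Section 3.2.1.2.** "Subjects who have neither completed DLT evaluation nor experienced DLT will not be included in a BLM update". Only a subject who meets neither condition is left out.
- **DLT-Evaluable Set, Section 11.2.** It takes subjects "who had at least one DLT during the 7 days of Cycle 0 or the 21 days of Cycle 1", and separately those who "did not have a DLT but received at least 75% of the doses in the 21 days of Cycle 1". The dose condition sits only in the second branch.

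Section 11.2 also counts doses over Cycle 1 alone, whereas the Section 3.2.1.3 row counts Cycle 0 and Cycle 1.

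**The concern.** Take a subject who has a DLT early in the 28-day window and then stops dosing for a reason that is not an adverse event. Section 3.2.1.3 puts this subject outside the evaluable group. Sections 3.2.1.2 and 11.2 put the subject inside it, counted as a DLT. No sentence ranks the two rules.

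The row is where site staff are likely to look. The visit procedures in Section 6.1 send investigators to Section 3.2.1.3 to judge whether an event is a DLT.

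Leaving for progression can be read as a non-AE reason, because Sections 9.1 and 9.5 say progression is not reported as an AE unless the subject dies of it with no other cause.

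The cohorts are small (minimum three evaluable subjects) and Section 1.1.3 reports no clinical data for DS-1205c. One DLT therefore carries much weight in the model, and leaving it out always lowers the estimated DLT rate.

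**Working it through.** **1. The rules applied to the same subject** (DLT in the window, more than 25% of doses missed for a non-AE reason)

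| Source | Status |
|---|---|
| 3.2.1.3, last row of the not-DLT table | not evaluable |
| Synopsis and 3.2.1.2, evaluability | evaluable |
| 3.2.1.2, model update | included |
| 11.2, DLT-Evaluable Set | included |

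**2. When the 25% threshold is crossed.** Scheduled DS-1205c doses: 28 days × 2 = 56, and 0.75 × 56 = 42, the figure printed in Section 3.2.1.3. For gefitinib, 0.75 × 21 = 15.75, rounded up to the printed 16. A last dosing day of Day 21 gives 42 doses taken and 14 missed, 14/56 = 25.0%, not over the threshold. Day 20 gives 16 missed, 16/56 = 28.6%, over it. Only doses missed for non-AE reasons count.

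**3. Model inputs** (Sections 11.11.1 to 11.11.3)

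- logit π(d) = log α + β log(d/800), with d read as mg per BID dose.
- (log α, log β) bivariate normal: means (−1.1493, −0.5514), SDs (2.0739, 1.5228), correlation −0.1943.
- A dose is admissible if P(DLT rate > 0.33) < 0.25. Among admissible doses, the model takes the one with the highest probability of a rate in 0.16–0.33.

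The posterior is proportional to the prior × Π π(d)^x (1 − π(d))^(n − x), for x DLTs in n subjects at each dose. It was integrated on a 1201 × 1201 grid over ±6 SD.

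**4. The plan's own figure.** At 800 mg the slope term is zero, so the prior median is 1/(1 + e^1.1493) = 24.1%, against the stated approximately 24.5%. At 200 mg the grid gives 8.0%, against approximately 8%. The prior reproduces.

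**5. One DLT kept or left out.** Cohort outcomes are illustrative. Entries are P(DLT rate > 0.33).

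| History | Dose examined | Kept, 1/3 | Left out, 0/2 | Left out, further DLT-free subject, 0/3 |
|---|---|---|---|---|
| First cohort at 200 mg | 200 mg | 0.368 | 0.065 | 0.037 |
| 0/3 at 200; cohort at 400 mg | 600 mg | 0.292 | 0.065 | 0.049 |
| 0/3 at 200 and 400; cohort at 600 mg | 800 mg | 0.263 | 0.081 | 0.069 |
| 0/3 at 200, 400 and 600; cohort at 800 mg | 800 mg | 0.132 | 0.023 | 0.014 |

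- Row 1: kept, no provisional dose is admissible. Left out, all four are, and the model selects 800 mg.
- Row 2: kept, 600 mg is barred and the model selects 400 mg. Left out, 600 mg is admissible and the model selects 800 mg.
- Row 3: kept, 800 mg is barred and the model selects 600 mg. Left out, it selects 800 mg.
- Row 4: 800 mg is selected either way.

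The 0/2 column falls short of the three evaluable subjects needed before escalating, so enrollment at that dose would have to continue first.

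**6. Same subjects under both rules.** If a fourth, DLT-free subject has been treated, the comparison is 1/4 against 0/3. Row 1: P at 200 mg is 0.254 with the DLT kept, so still no admissible dose, but only just. Row 2: P at 600 mg is 0.232, so 600 mg is admissible and selected, against 800 mg with the DLT left out. Row 3: P at 800 mg is 0.217, and 800 mg is selected either way.

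**The case against.** The strongest reply is that the protocol already says who enters the model. The update rule in Section 3.2.1.2 is the only sentence that states who is left out, and a subject with a DLT is not. Section 11.2 agrees. The disputed row can also be read as the counterpart of the rule that failing to complete 75% of doses because of a Grade ≥ 2 AE is itself a DLT: the same shortfall for other reasons is not a DLT and leaves the subject unassessed. On that reading it was never meant to erase an observed toxicity.

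This largely stands as to intent. It does not cure the wording, which is unqualified.

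The reply on frequency also stands:

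- Holds triggered by a DLT (Section 5.4.1) are AE-related and do not count towards the 25%.
- Subjects are in hospital from Cycle 0 Day 2 to Cycle 2 Day 2, with leave possible only after Cycle 1 Day 8 (Section 6.1), which limits noncompliance.
- The first scheduled scan is six weeks after Cycle 1 Day 1 (Section 6.1.3.5), so leaving for radiological progression inside the window needs an unscheduled scan.
- DLTs are communicated in real time (Section 3.2.1.4), and the sponsor weighs toxicity data as well as the model (Section 3.2.1.2). The event would still be seen.

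A reader might take the flare figure in Section 1.2.1, up to 23% with median onset at 8 days, as the share of DLTs at risk. It is a rate of tumor flare after TKI withdrawal, not of leaving treatment, and still less of leaving after a DLT for an unrelated reason. The documents give no basis for an exposure rate. A reader might also infer that the excluded subject is replaced. No replacement rule is stated; the 0/3 column assumes that a further DLT-free subject is enrolled.

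**Conclusion.** The contradiction is real and in the current text: one row excludes a subject with an observed DLT whom the evaluability definition, the model-update rule and the analysis-set definition all include.

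A reader might conclude that the plan discards observed DLTs. The documents do not support that. The DLT is lost only if Section 3.2.1.3 is applied literally against the other two sections, and only for a subject with both a DLT and more than 25% of doses missed for a non-AE reason.

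When it occurs, the error runs towards higher doses and can change the model's recommendation. The clearest case is a first cohort at 200 mg: 0.37 and no admissible dose with 1/3, against 0.065 or 0.037 and four admissible doses with the subject left out. The size depends on the history and on the comparison. It shrinks when a fourth treated subject is counted under both rules, and the recommendation is unchanged for one DLT in three at 800 mg after clean lower cohorts (0.13 against 0.01).

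These figures rest on the printed prior, d taken as mg per BID dose, and illustrative cohort outcomes. This is an inexpensive correction of an internal inconsistency, worth making before the next model update, but not a critical defect.

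**What to change.** Reconcile the passages:

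1. Limit the last row of the not-DLT table in Section 3.2.1.3 to subjects who have not had a DLT, as Section 11.2 already does with its dose condition.
2. State that a subject with a DLT in the window stays in the DLT-Evaluable Set and in every BLRM update, whatever the later dosing or reason for leaving.
3. Move the sentence out of the table of events that are not DLTs, next to the evaluability definition.
4. At the same time, align the dosing window (Cycle 0 plus Cycle 1, or Cycle 1 alone) between Sections 3.2.1.3 and 11.2.

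The cost is a short wording change to the protocol. It needs no extra subjects, visits or data.
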